2.2 Secondary Objectives

Objective: Assess the safety and tolerability of pembrolizumab in combination with chemotherapy in the frontline setting.

Hypothesis: The combination of pembrolizumab with AVD as frontline treatment will be well tolerated. Furthermore, the addition of standard chemotherapy utilizing an age and stage-adjusted approach will result in an increased number of patients with PET-negativity at interim PET, and the ability to limit the number of cycles of chemotherapy, and further reduce the need for radiation therapy, thereby minimizing acute and chronic toxicity

Objective: Determine the extent of FDG uptake, using a semi-quantitative approach (eg, Deauville score), after pembrolizumab induction, and after subsequent chemotherapy.

Hypothesis: The percentage of patients with a Deauville score of 1-2 after pembrolizumab alone will be 50%. The percentage of patients with a Deauville score of 1-2 following two cycles of chemotherapy will exceed 75%.

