4.3.1 Pembrolizumab Dose Modifications

Adverse events (both non-serious and serious) associated with pembrolizumab exposure may represent an immunologic etiology. These adverse events may occur shortly after the first dose or several months after the last dose of treatment. Pembrolizumab must be withheld for drug-related toxicities and severe or life-threatening AEs as per table 4.1 below. See Section 4.5.3 for supportive care guidelines, including use of corticosteroids.

Initial Version date: March 10th, 2017

Amendment 6: March 20th, 2010

Amendment 6: March 29th, 2019

Table 4.1: Dose Modification Guidelines for Pembrolizumab-Related Adverse Events

General instructions:

- Corticosteroid taper should be initiated upon AE improving to Grade 1 or less and continue to taper over at least 4
 weeks.
- 2. For situations where pembrolizumab has been withheld, pembrolizumab can be resumed after AE has been reduced to Grade 1 or 0 and corticosteroid has been tapered. Pembrolizumab should be permanently discontinued if AE does not resolve within 12 weeks of last dose or corticosteroids cannot be reduced to ≤10 mg prednisone or equivalent per day within 12 weeks.
- 3. For severe and life-threatening irAEs, IV corticosteroid should be initiated first followed by oral steroid. Other immunosuppressive treatment should be initiated if irAEs cannot be controlled by corticosteroids.
- 4. For signs or symptoms of Stevens-Johnson Syndrome (SJS) or Toxic Epidermal Necrolysis (TEN), withhold pembrolizumab and refer the patient for specialized care for assessment and treatment.

pembrolizumab and refer the patient for specialized care for assessment and treatment.				
Immune-related AEs	Toxicity grade or conditions (CTCAEv4.03)	Action taken to pembro	irAE management with corticosteroid and/or other therapies	Monitor and follow-up
Pneumonitis	Grade 3 or 4, or recurrent Grade 2	Withhold Permanently discontinue	Administer corticosteroids (initial dose of 1-2 mg/kg prednisone or equivalent) followed by taper	Monitor participants for signs and symptoms of pneumonitis Evaluate participants with suspected pneumonitis with radiographic imaging and initiate corticosteroid treatment Add prophylactic antibiotics for opportunistic infections

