Grades 3 or 4 Grade 3: Prolonged (i.e., not rapidly responsive to symptomatic medication and/or brief interruption of infusion); recurrence of symptoms following initial improvement; hospitalization indicated for other clinical sequelae (e.g., renal impairment, pulmonary infiltrates) Grade 4: Life-threatening; pressor or 33rticarial support indicated	Stop Infusion. Additional appropriate medical therapy may include but is not limited to: IV fluids Antihistamines NSAIDS Acetaminophen Narcotics Oxygen Pressors Corticosteroids Epinephrine Increase monitoring of vital signs as medically indicated until the subject is deemed medically stable in the opinion of the investigator. Hospitalization may be indicated. Subject is permanently discontinued from further trial treatment administration.	No subsequent dosing

Amendment 6: March 29th, 2019

Initial Version date: March 10th, 2017

4.5.2 **Management of Cardiac Toxicities**

During treatment with pembrolizumab, patients will be closely monitored for cardiac toxicities. For patients with evidence of congestive heart failure. myocardial infarction, cardiomyopathy, or myositis, cardiac evaluation should take place including lab tests and cardiology consultations as clinically indicated including ECG, CPK, troponin, and ECHO.

Pembrolizumab dosing should be modified according to Table 4.5.

Table 4.4 – Management of Cardiac Toxicities			
Cardiac *	Management/Next Dose for Pembrolizumab Cardiac Toxicities		
≤ Grade 1	Hold dose pending evaluation and observation.** Evaluate for signs and symptoms of CHF, ischemia, arrhythmia or myositis. Obtain history EKG, CK (for concomitant myositis), CK-MB. Repeat troponin, CK and EKG 2-3 days. If troponin and labs normalize may resume therapy. If labs worsen or symptoms develop then treat as below. Hold pending evaluation		
Grade >2 with suspected myocarditis	Hold dose.** Admit to hospital. Cardiology consult. Rule out MI and other causes of cardiac disease. Cardiac Monitoring. Cardiac Echo. Consider cardiac MRI and cardiac biopsy. Initiate high dose methylprednisolone. If no improvement within 24 hours, add either infliximab, ATG or tacrolimus. Consult algorithm for more details. Resume therapy if there is a return to baseline and myocarditis is excluded or considered unlikely.		

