10.3.2 Analytic Plan for Secondary Objectives

To assess safety and tolerability, all adverse events will be summarized in terms of type, grade, timing and attribution to treatment. All enrolled patients who receive at least one injection of study drug or undergo a study-related procedure will be included in the safety analysis. The highest toxicity grades per patient will be tabulated for AEs and laboratory measurements, and the number and percent of patients reporting AEs will be quantified. Listings will be required for all on-study deaths, SAEs and AEs that lead to withdrawal from study. Narratives for all SAEs and deaths on-study will be required. These summaries will be done by age cohort.

Continuous toxicity monitoring will occur using the method of Ivanova et al.⁵¹ While this method may be used to identify an unacceptable level of toxicity after each patient, only values for every 5 patients will be given here. The following table gives the number of unacceptable toxicities that need to be observed after 5, 10, 15, 20, 25, 30 patients to identify an adverse toxicity rate exceeding 20% with a false positive rate (after each patient) of 2% and a desired probability of early stopping of 5%. Unacceptable toxicity is defined as any toxicity requiring discontinuation of pembrolizumab, as defined in Table 4.1.

Number of patients observed: 5 10 15 20 25 30 Number of observed toxicities: 4 6 8 9 11 12

Response assessment: Anti-tumor activity will be assessed using the LUGANO 2014 Response Criteria (Appendix C). Patients who receive consolidation with pembrolizumab will also have disease assessed by the Immune Response Criteria (Appendix F) as an exploratory assessment. To assess progression free survival

(PFS) and overall survival (OS), Kaplan Meier curves for progression and survival will be calculated for each cohort. The 3-year PFS will be determined from this curve for all patients

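### The toxicity stopping boundary counts only Table 4.1 discontinuations, so infusion-reaction discontinuations, Grade 5 events as such and, read literally, immune events after the last planned pembrolizumab dose do not count toward it

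*Combined protocol and SAP*

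**What the plan says.** Section 10.3.2 monitors toxicity after every patient. The reference is a toxicity rate of 20%, with a pointwise false positive rate of 2% and an overall early-stopping probability of 5%. The printed boundary is 4, 6, 8, 9, 11 and 12 events after 5, 10, 15, 20, 25 and 30 patients. The counted event is defined in one sentence: "Unacceptable toxicity is defined as any toxicity requiring discontinuation of pembrolizumab, as defined in Table 4.1". No observation window is given for the rule.

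Table 4.1 (Section 4.3.1) lists pembrolizumab-related, mainly immune-related, events. Its permanent-discontinuation criteria are stated grades up to Grade 4, certain recurrences, and failure to resolve or to taper steroids within 12 weeks. For Grade 3-4 hypophysitis and hyperthyroidism, a footnote leaves the choice between withholding and discontinuing to the investigator. The introduction to the table says of immune events: "These adverse events may occur shortly after the first dose or several months after the last dose of treatment".

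Infusion reactions are handled separately in Table 4.3 (Section 4.5.1). For Grade 3 or 4 it states: "Subject is permanently discontinued from further trial treatment administration". It also requires permanent discontinuation for Grade 2 reactions that occur despite premedication.

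All patients receive three induction doses, on days 1, 22 and 43 (Sections 4.2.1 and 5.0). Only selected patients aged 60 or older receive more (Section 4.2.3). The safety objective in Section 2.2 is to "Assess the safety and tolerability of pembrolizumab in combination with chemotherapy in the frontline setting".

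**The concern.** The rule borrows its event definition from a table written to guide dosing. A dosing table needs to cover only events after which the next dose is in question. A stopping rule needs to cover every event of the kind it is meant to limit, and the two sets differ here.

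If the rule is followed to the letter, some pembrolizumab toxicities as severe as those it counts add nothing to the tally. The boundary is then slower to signal than its stated operating characteristics suggest. The wording is also open enough that two monitors could count the same late immune event differently. The deaths, SAEs and withdrawals listed elsewhere in 10.3.2 carry no numerical threshold, so nothing else in the plan makes up for a low count.

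**Working it through.** **1. Reproducing the boundary.** For each n from 1 to 30, take the smallest r with P(X ≥ r) ≤ a, where X ~ Binomial(n, 0.20). Choose the largest a, on a grid of 0.0001, for which the exact probability of ever crossing within 30 patients at a 20% rate is at most 5%. This gives a = 0.0173 and an overall probability of 0.0495. At 5, 10, 15, 20, 25 and 30 patients the boundary is 4, 6, 8, 9, 11 and 12, exactly as printed. A pointwise level of exactly 0.02 gives 4, 6, 7, 9, 10 and 12 with an overall probability of 0.0599, so the 5% limit is the one that binds. The printed figures are sound; the question is only what is counted.

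**2. Comparing the definition with the rest of the protocol.**

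| Event | Where it is handled | Counted under 10.3.2 as written? |
|---|---|---|
| Grade 3-4 infusion reaction, or Grade 2 despite premedication | Table 4.3, permanent discontinuation | No; only Table 4.1 is cited |
| Fatal immune event | Grade 5 is a separate grade (Section 7.2.2); no Grade 5 row in Table 4.1 | Not stated; possibly through an earlier Grade 4 stage |
| Death attributed to AVD alone | Outside Table 4.1 | No |
| Immune event at a discontinuation grade after the last planned dose | Expected in Section 4.3.1 | Not literally, since no dose remains to discontinue; yes if the rule means that the grade is met |
| Grade 3-4 hypophysitis or hyperthyroidism | Table 4.1, investigator's discretion | Depends on the investigator's choice |

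The fourth row concerns every patient under 60, and any patient of 60 or older who does not qualify for consolidation, from day 43 onward.

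**3. What undercounting does to the boundary.** If the true rate of unacceptable toxicity is p and a share m goes uncounted, the boundary sees events at rate p(1 − m). Using the 30-look boundary from step 1:

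| True rate p | m = 0 | m = 10% | m = 25% | m = 50% |
|---|---|---|---|---|
| 40% | 0.695 | 0.537 (seen rate 36%) | 0.293 (30%) | 0.050 (20%) |
| 30% | 0.293 | 0.192 (27%) | 0.086 (22.5%) | 0.013 (15%) |

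Neither p nor m is given in the documents. The table shows how sensitive the rule is; it is not a forecast.

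**4. What a wider definition does.** With the boundary unchanged, the chance of crossing is 0.0495 at a counted rate of 20%, 0.138 at 25% and 0.293 at 30%.

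**The case against.** The strongest reply is that the definition can be read as covering any toxicity that meets a Table 4.1 discontinuation grade, whether or not doses remain. Section 4.3.1 supports this. It introduces the table by noting that events may come late, and it measures non-resolution over 12 weeks from the last dose. From day 43 that runs to day 43 + 84 = 127, past AVD cycles 1 and 2 (days 64 to 120). For an older patient who may go on to consolidation, an event during AVD can still cancel planned doses. This reading is plausible, but the text does not choose it. It also leaves the infusion-reaction gap untouched.

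A second reply is that the rule monitors the investigational drug, and AVD is standard chemotherapy. That is a legitimate design choice. Leaving non-fatal AVD toxicity out of the count is not an error.

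A third is that other oversight exists. All SAEs go to the monitor within 24 hours and to the DSMC at its next meeting (Section 7.3.3). The DSMC reviews aggregated safety data (Section 7.4.4), and deaths and SAEs are listed and narrated (Section 10.3.2). A reader might infer that the AVD period is invisible to safety monitoring, or that a harmful sequence could run unnoticed to full enrolment. The documents do not support either inference. What stands is narrower: those channels have no numerical threshold.

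A fourth is that the illustrated rates are high against the protocol's own data. Section 1.2.1 reports one of 15 pembrolizumab patients with a grade 3-5 event, and drug-related grade 3 events in 22% of nivolumab patients. This is fair, and the illustration should carry no more weight than that.

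**Conclusion.** The point holds as a gap in the event definition. Omitting Table 4.3 discontinuations is plain on the text. Grade 5 is not named. Late immune events are missed on the literal wording and counted on a reasonable alternative, and the plan does not say which applies. Discretionary rows let identical events count differently.

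The loss cannot be sized from the documents. If the true rate were 40%, missing 10% of events would cut the chance of crossing from about 70% to 54%, and missing 25% would cut it to 29%. Both the rate and the missed shares are assumptions. The figures also assume a look after every patient up to 30 and independent events at a constant rate.

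Because following the rule as written leads to undercounting, and the remedy is small, the sponsor should make the change. The boundary itself needs no correction.

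**What to change.** In Section 10.3.2, define the counted event as any toxicity at least possibly related to pembrolizumab that meets a permanent-discontinuation criterion of Table 4.1 or Table 4.3, whether or not pembrolizumab doses remain. Add any Grade 5 event at least possibly related to study treatment. Apply the existing collection windows: adverse events to 30 days and SAEs to 90 days after the last study treatment.

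Two further statements are needed from the sponsor:

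- How the rows that leave withholding or discontinuing to the investigator are counted, fixed in advance. Table 4.1 allows pembrolizumab to resume after some of these events, so whether they are unacceptable is for the sponsor to decide.
- Whether 20% remains the right reference rate for the wider definition. If so, the printed boundary stands; if not, it should be recomputed.

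The attribution requirement matters. Without it, a Grade 3 transaminase rise caused by dacarbazine, which Section 8.4.9 lists as a side effect, would count against pembrolizumab.

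The cost is one paragraph. The events are largely collected already, though non-serious events later than 30 days after treatment would remain outside. The price is a somewhat higher chance of crossing: 5% at a 20% rate, and about 14% if the wider definition raises the rate to 25%. Only the counting changes; no change to patient management is proposed.

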consolidation treatment with pembrolizumab for 2 years total (3 doses in induction + 32 doses in consolidation). Those with

	Deauville 1, 2, 3 (PET#3) will continue to follow-up if they receive all 6 AVD doses successfully. If they were unable to receive the full intended 6 cycles of chemotherapy for stage III/IV disease because of poor tolerance, they should receive consolidation with pembrolizumab for up to 1 year (3 doses in initiation + 14 doses in consolidation).
	Total Study Duration: 9 weeks of initiation therapy with pembrolizumab + 16-24 weeks of chemotherapy + consolidation for up to 96 weeks (select elderly patients) + 2 years of follow-up
Statistical Methodology	The treatment paradigm of this trial will be considered worthy of further evaluation if at least 40% of patients achieve CR at PET#2 (defined as Deauville 1-3). In order to have 84% power to detect an increase from the historical control of 20% rates of CR for patients with rel/ref cHL treated with pembrolizumab, at a one-tailed alpha of 10%, approximately 26 evaluable patients will be required total. The accrual goal is 30 patients to account for possible unevaluable patients.

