4.2.2 Standard Chemotherapy

4.2.2.1 Cycle 1 & 2: AVD chemotherapy post pembrolizumab "lead in" Treatment should be administered on day 1 of each 28 day cycle after all procedures/assessments have been completed as detailed

on the Study Procedures Table (Section 5.0). Trial treatment may be administered up to 3 days before or after the scheduled Day 1 of each cycle due to administrative reasons.

Doxorubicin (Adriamycin) 25 mg/m², vinblastine 6 mg/ m², and dacarbazine 375mg/ m² will be on day 1 and 15 of a four week cycle.

- All patients will receive treatment with 2 cycles of AVD.
- Treatment will commence 21 days after final dose of induction pembrolizumab, but not prior to PET #2 (+/- 3 days). Treatments will be on days 1 and 15 of a 28-day cycle.
- PET-CT (PET#3) should occur on day 117-120, or day 26-29 of AVD cycle 2 as listed in section 5.0.

AVD supportive care measures

Pre-medications:

We recommend patients receive pre-treatment with acetaminophen 650 mg po and diphenhydramine 50 mg po given 30 minutes prior to AVD as per institutional protocol.

Prophylactic antibiotics:

Prophylactic antibiotic use (e.g., Levaguin, nystatin) is at the discretion of the treating physician.

Growth factor protocol:

In elderly patients granulocyte colony stimulating factor (e.g., G-CSF) is recommended and in accordance with ASCO guidelines. Please record all granulocyte (or erythrocyte) colony stimulating factors on the treatment forms.

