4.6.2 Duration of Follow Up

Once patients are off treatment for any reason, they will have a final off-treatment visit approximately 30 days post-last dose of study therapy. Thereafter, they will be followed with at least one clinic visit every 3 months for up to 2 years from end of treatment. Patients removed from treatment for unacceptable adverse events will be followed until resolution or stabilization of the adverse event.

For patients who undergo allogeneic stem cell transplant (SCT) within 2 years of study treatment, transplant parameters and adverse events will be recorded as detailed in section 4.6.3.

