4.6.3 Subject Withdrawal/Discontinuation Criteria from Treatment and/or Overall Study

Subjects may withdraw consent at any time for any reason or be dropped from the trial at the discretion of the investigator should any untoward effect occur. In addition, a subject may be withdrawn if enrollment into the trial is inappropriate, the trial plan is violated, or for administrative and/or other safety reasons. Specific details regarding discontinuation or withdrawal are provided in Table 4.1.

A subject must be discontinued from the trial for any of the following reasons:

- Patient voluntarily withdraws from treatment (follow-up permitted)
- The subject or legal representative (such as a parent or legal guardian) withdraws consent (no follow-up permitted).
- Confirmed radiographic disease progression
- Note: For unconfirmed radiographic disease progression, please see Section 5.1.6
- Unacceptable toxicity/adverse experiences as described in Section 4.4
- Intercurrent illness that prevents further administration of treatment
- Investigator's decision to withdraw the subject (i.e. continuation not in the patient's best interest)
- The subject has a confirmed positive serum pregnancy test
- Patient develops a second malignancy that requires treatment which would interfere with this study
- Noncompliance or inability to comply with trial treatment or procedure requirements
- The subject is lost to follow-up
- Administrative reasons

The End of Treatment and Follow-up visit procedures are listed in Section 5 (Protocol Flow Chart). After the end of treatment, each subject will be followed for 30 days for adverse event monitoring (serious adverse events will be collected for 90 days after the end of treatment as. Subjects who discontinue for reasons other than progressive disease will have post-treatment follow-up for disease status until disease progression, initiating a non-study cancer treatment, withdrawing consent or becoming lost to follow-up. After documented disease progression each subject will be followed by telephone for overall survival until death, withdrawal of consent, or the end of the study, whichever occurs first.

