6.4.4 Progression Free Survival (PFS)

PFS will be defined as the length of time from treatment on protocol until the first occurrence of disease relapse, progression, re-initiation of cytotoxic chemotherapy, or death due to disease, or until last contact if the patient did not experience any of these from the end of treatment through two years of follow up.

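### 3-year PFS is promised for all patients, but under the two-year post-treatment limit completers without consolidation are observed for only about 2.4–2.7 years

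*Combined protocol and SAP*

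**What the plan says.** Section 10.3.2 plans Kaplan-Meier curves for PFS and OS and adds: "The 3-year PFS will be determined from this curve for all patients".

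Section 6.4.4 starts PFS at treatment on protocol, and for patients without an event it refers to the period "from the end of treatment through two years of follow up". The other follow-up provisions are:

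- **Study Summary, Total Study Duration:** "9 weeks of initiation therapy with pembrolizumab + 16-24 weeks of chemotherapy", then "consolidation for up to 96 weeks (select elderly patients) + 2 years of follow-up".
- **Section 4.6.2:** once off treatment for any reason, "they will have a final off-treatment visit approximately 30 days post-last dose of study therapy"; after that, "they will be followed with at least one clinic visit every 3 months for up to 2 years from end of treatment".
- **Section 5.0, footnote 7:** survival contact for two years from the last dose of study drug, by clinic visit or telephone.
- **Section 4.6.3:** "Subjects who discontinue for reasons other than progressive disease will have post-treatment follow-up for disease status until disease progression", or until non-study cancer treatment, withdrawal of consent or loss to follow-up. No time limit is given.

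Section 4.2.3 restricts consolidation to patients aged 60 or older who have a positive PET#3, or who have stage III/IV disease, a negative PET#3 and fewer than the planned six AVD cycles. The chemotherapy-intolerance paragraph in Section 4.3.2 also allows consolidation for intolerant patients in PR or CR, and states no age or stage limit there.

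**The concern.** A landmark for all patients needs follow-up that can reach it in all the main treatment paths. Here the length of observation depends on the length of treatment, because the two-year clock starts when treatment ends. Patients who receive only induction and AVD finish treatment well inside the first year, so two further years do not bring them to year three.

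If the two-year limit governs, the event-free patients on those paths are censored before 3 years. The last part of the curve then describes mainly consolidation recipients, who are selected by age, PET#3 result or chemotherapy tolerance, yet the figure would be labelled as applying to everyone. If few or none receive consolidation, the curve has little or no support at 3 years. Two analysts could also apply different censoring rules, one following Section 6.4.4 and the other Section 4.6.3.

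**Working it through.** **Inputs.** Induction is 3 × 21 days = 9 weeks (Section 4.2.1). AVD cycles last 28 days: "Treatments will be on days 1 and 15 of a 28-day cycle" (Section 4.2.2). The planned number of AVD cycles is k = 4 to 6. The off-treatment visit is about 30 days (4.3 weeks) after the last dose. Follow-up is 2 years = 104 weeks. The PFS origin is read as the first dose.

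**The plan's own durations reproduce.** 4–6 cycles × 4 weeks = 16–24 weeks. 32 consolidation doses × 3 weeks = 96 weeks. AVD cycle 3 starts on day 64 + 56 = 120, as in the Section 5.0 table.

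**Observation from first dose: no consolidation, no delays.** The documents do not fix when treatment ends, so three readings are shown.

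| End of treatment taken as | Formula (weeks) | k = 4 | k = 6 |
|---|---|---|---|
| Last AVD dose (day 15) | 9 + 4(k−1) + 2 + 104 | 127 (2.43 y) | 135 (2.59 y) |
| End of last cycle | 9 + 4k + 104 | 129 (2.47 y) | 137 (2.63 y) |
| 30-day visit | last-dose result + 4.3 | 131.3 (2.52 y) | 139.3 (2.67 y) |

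Years = weeks × 7 / 365.25. The shortfall against 156 weeks runs from 156 − 139.3 = 16.7 to 156 − 127 = 29 weeks. Stopping after two AVD cycles gives 119, 121 or 123.3 weeks on the same three readings (2.3–2.4 years).

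**Patients under 60 moved to escBEACOPP.** The lengths of escBEACOPP cycles and radiotherapy are not stated. PET#3 falls at about week 9 + 8 = 17. To be observed to week 156, treatment would have to end at week 156 − 104 = 52. That means 52 − 17 = 35 weeks of treatment after PET#3, or 35 − 4.3 = 30.7 weeks if the clock starts at the 30-day visit. The Study Summary's 16–24 weeks of chemotherapy, less 8 weeks of AVD, leaves 8–16 weeks.

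**Patients given full consolidation.** Section 4.2.3 starts it 4 weeks after day 1 of the final AVD cycle, so the last dose falls at week 9 + 4k + 3(d − 1) for d doses.

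- 14 doses after 2–5 AVD cycles: last dose at week 56–68, observation 160–172 weeks (3.07–3.30 years).
- 32 doses after 4–6 AVD cycles: last dose at week 118–126, observation 222–230 weeks (4.26–4.41 years).

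These patients do pass 3 years.

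**Effect of delays.** Section 4.3 has interrupted treatment delayed and still given in full. Table 4.1 allows pembrolizumab to be withheld for up to 12 weeks from the last dose, which is 12 − 3 = 9 weeks beyond the interval. Section 4.3.2 requires PI approval only for AVD delays beyond 5 weeks from the last dose, so 5 − 2 = 3 extra weeks per dose are possible without it. One such hold plus three or four such delays adds 9 + 9 = 18 to 9 + 12 = 21 weeks. A six-cycle patient needs 156 − 139.3 = 16.7 to 156 − 135 = 21 weeks, so that patient could reach 3 years.

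**A 2-year landmark.** The earliest possible end of treatment is the first dose, and 0 + 104 = 104 weeks. Two years from first dose therefore lies within planned follow-up under either rule.

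**The case against.** The strongest reply is that the follow-up rules may be compatible. Section 4.6.2 could cap only the quarterly clinic visits, and footnote 7 only survival contact, leaving Section 4.6.3 to govern disease status without a cap. The two-year clause in Section 6.4.4 is loosely worded and censors at last contact. On that reading 3 years may be reachable. This stands as a possibility, but it is not settled. Section 4.6.3 speaks of subjects who discontinue, and its list of reasons does not include completing treatment. Section 4.6.2 applies to patients off treatment for any reason, and the Study Summary gives total duration with two years of follow-up.

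A reader might infer that 3-year PFS cannot be estimated, or that only consolidation recipients can be at risk at 3 years. The documents support neither. Kaplan-Meier handles staggered censoring, consolidation recipients remain under observation, and long permitted delays could carry an occasional other patient to 3 years. A reader might also infer bias in a known direction. The number who will receive consolidation is not given, so neither size nor direction can be stated.

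The stakes are limited. Section 2.2 does not list PFS among the secondary objectives, Section 10.0 calls the efficacy data preliminary, and no test or threshold uses 3-year PFS. A thin tail would show in the number at risk. This argues for a modest correction, but the conflict remains.

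Finally, a 2-year landmark still depends on disease status being recorded at follow-up visits. The Survival Follow-Up column in Section 5.0, as extracted, marks only post-study therapy, survival status and adverse events. Because the extracted table may be broken, this is weak evidence, but the point should be made explicit.

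**Conclusion.** The concern holds. Under the two-year limit, event-free patients who complete 4–6 AVD cycles without consolidation or delays are observed for about 127–139 weeks (2.4–2.7 years), 17–29 weeks short of the promised landmark. Apart from occasional patients with long delays, the 3-year estimate would rest on consolidation recipients: selected patients aged 60 or older under Section 4.2.3, and possibly chemotherapy-intolerant patients under Section 4.3.2. Those two sections differ on who may receive consolidation and must be reconciled.

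This rests on reading the PFS origin as the first dose and on the two-year limit governing disease status. If Section 4.6.3 governs and covers completers, 3 years may be reachable. The documents do not say which rule applies. The primary endpoint is unaffected and PFS drives no decision, so the change is advisable but modest.

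**What to change.** 1. Reconcile the Study Summary, Section 4.6.2, Section 5.0 footnote 7 and Section 6.4.4 with Section 4.6.3. The result should be one disease-status follow-up limit, stated to apply or not to patients who complete treatment, and one PFS censoring rule.
2. Unless uncapped follow-up is confirmed to cover completers, replace 3-year PFS in Section 10.3.2 with 2-year PFS from start of treatment (Kaplan-Meier estimate, 95% confidence interval, number at risk at 2 years). If it is confirmed, keep 3-year PFS and report the number at risk at 3 years.
3. State that disease status is recorded at the existing 3-monthly clinic visits.
4. Reconcile Section 4.2.3 with the chemotherapy-intolerance paragraph of Section 4.3.2 on who may receive consolidation.

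**Cost.** A wording change in Section 10.3.2 and a few clarifying sentences, with no clinic visits beyond those in Section 4.6.2. The downside is a shorter landmark. If the two-year limit governs and the sponsor prefers to keep 3 years, each completer without consolidation would need about 17–29 more weeks of disease-status follow-up, or two to three quarterly visits.
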